During Phase 1, we will work with the social work representatives from each of the two participating local authorities, Glasgow, and Bromley, to establish how our RCs will establish our target population. The parents of any child in these local authorities who meets our criteria and is aged 0-60 months will be approached by our RCs to discuss the study. If they consent, families will be invited for baseline research assessments (usually remote but face-to-face assessment if preferred). Thereafter the family will be randomised to IPS or services-as-usual and followed up at six months post randomisation. Participants will receive a voucher for taking part in research interviews. Parent Collaborators will help us develop ways of supporting all participants including any who withdraw. We will also draw on existing assets such as NSPCC helpline and Local Authority partners for any safeguarding concerns. Further purposive sampling from this group of 30 families will allow us to explore specific questions arising in our qualitative process evaluation.

Trial Recruitment

- Trial population
 - Families in the Glasgow or London (Bromley) trial sites where all children in the household are aged 0-5 years and the family has an allocated social worker plus a multi-agency support plan.

- Inclusion and exclusion criteria
 - Inclusion criteria: Families in the Glasgow or London trial sites where all children in the household are aged 0-5 years and the family has an allocated social worker plus a multi-agency support plan.
 - Exclusion criteria:
 - If the child has a Child Protection Plan or is on the Child Protection Register
 - If the family are in the process of 'stepping down' from a CPP or CPR
 - If the child is currently engaged in therapeutic work

- Identifying and approaching participants
 - Pathways into trial have been defined collaboratively with Parent Collaborators, local authority partners in Glasgow and Bromley and the IPS teams and are illustrated on the following page.

Potential participants may be identified by social workers or other support services, with the referral needing to be submitted by the family's social worker. Consent will be required from the family for their referral to be submitted. Recruitment Coordinators will work with organisations to identify the target population, screen for eligibility and facilitate referrals to the study. Potential participants will then receive a participant information sheet and consent form by mail, and a follow-up telephone call from the trial office to review the information sheet and respond to any comments or questions.

Screening for eligibility

Referring Social Workers & Research Coordinators will screen potential participants for eligibility using a list of eligibility criteria provided by the trial office. To ensure inclusion/exclusion criteria are met, the researcher will also confirm potential participants' eligibility during the first phone call (see below).

Informed consent

Potential participants identified by the referring Social Worker will receive a participant information sheet (PIS), Privacy Notice and consent form and will be asked to give their consent before a referral is passed to the study. Following randomisation, potential participants who have been selected for inclusion in the trial will receive an information sheet, Privacy Notice, and a consent form for participation in the trial. A follow-up telephone call from the trial office will take place within one week of receipt of PIS. Having reviewed the information sheet during this phone call, consenting participants will be asked to return the freepost consent form and an appointment will be made to collect baseline data by the UoG research team. Should the consent form not be returned by post, this will be completed during baseline data collection. The participant will have an opportunity to ask as many questions as needed and will be invited to contact the researcher (using info on the PIS) with any further queries. It will be made clear to participants that their involvement is entirely voluntary, and they can opt out or withdraw at any time.

Randomisation and allocation

Once baseline data is collected, participants will be randomised. A central randomisation facility will randomise patients (1:1) to IPS or SAU. The randomisation list will be created by a computer program written by a statistician who will have no involvement with the final analysis. The randomisation list, the program that generated it and the random seed used will be stored in a secure network location.

Administration arrangements post recruitment

The University of Glasgow trial office, and researchers at Queen Mary University London, will be responsible for the following:

- Arranging an appointment with the participants at a mutually convenient time and place (e.g., community health centre/participant's home or online) to collect baseline data
- Providing the randomisation facility with participant details
- Informing the participant and any referring organisation of the outcome of randomisation
- Informing the appropriate contact person from IPS of the outcome of randomisation
- Contacting parents to remind them of follow -up assessment
- Arranging an appointment with the participant to collect follow-up data

Post randomisation, arrangements for support will then be taken forward by respective services, and the trial team will not be involved.

Data Collection

Baseline

Measuring outcomes (putative outcome measures for a future definitive RCT - expected sample size for each measure ~30). As these are putative measures for a future definitive RCT, none of these measures are included in the study to measure any of our outcomes but simply to see if they are appropriate and acceptable for a future definitive RCT. We will be looking at basic aspects of the data from these measures, such as missingness of data, mean scores and standard deviations (to support sample size calculations for a future definitive RCT), and - qualitatively - at whether parents perceive the questions asked to be measuring the right kinds of things and are happy with the burden and have any other comments about acceptability.

Target	Measure	Source
Child mental health	RADA, SDQ, PIRGAS and Quality of life measure (PEDs-QL)	• Parent self-report questionnaires •Health routine data
Child material circumstances	Service use data	• Routine data

		
 • Parent interviews – including demographics, benefits etc • Social worker interviews
Parental mental health	GHQ and Quality of life measure (EQ-5D)	
 • Parent self-report questionnaires • Health routine data
Parental material circumstances	Service use data Parent-Reported Outcome Measure	
 • Routine data • Parent interviews including demographics, benefits, housing, employment etc • Social worker interviews • Co-created with parents to explore how service-focussed goals have been met
Parental experience of respect/stigma	Parent-reported Experience Measure	
 • Co-created with parents to explore how their goals have been met

After consent, we will arrange a baseline data collection appointment at a mutually convenient time, place and method. This may be conducted remotely if the participant prefers. This will involve the parent answering a semi structured interview (the RADA), and a number of multiple-choice questionnaires (as per table above) about their child and themselves. We will also ask them to record a ten-minute video of them interacting with their child. This session will last between 1-1.5 hours. We will be guided by the participant as to whether it makes sense to break this into more than one session or visit.

Qualitative interviews

Semi-structured interviews will be conducted in a separate session at a mutually convenient time and place by virtual or face to face methods. The entire sample will be asked to participate in interviews, but these will be optional and consented separately and will last up to an hour. It is possible that interviews may

explore some difficult experiences and participants could become upset. The researcher will be skilled and experienced in interviewing vulnerable people about potentially sensitive topics and will stop the interview if necessary, and only resume if the participant is happy to. The researcher will provide information on local support services if the participant is not receiving relevant help.

Video

Video collection will depend largely on the format of the baseline data collection visit. If the visit is in person, the researcher will seek to collect a video then and there. If the visit is being conducted remotely, we will seek to record the interaction via the method used (MS Teams) or, if that is not possible, we will ask the participant to record a video and send it to the research team via secure file transfer. Over the course of the Trial, we will establish which approach is most acceptable to participants.

Follow-up

Follow up data collection will mirror that of the baseline (Table 6.1) and will include the qualitative component. Follow up will take place 3-6 months after baseline and will allow us to track likely retention rates in a bigger trial.

End of Study

Participants will be contacted when the results of the study are published and will be provided with a summary of the results and publication details. We will work with Parent Collaborators to ensure accessibility of the summary findings.

Analysis

Qualitative analysis

The Process Evaluation forms a key part of this feasibility trial. It will explore and capture data on the process of coproduction of IPS, map out the context within which IPS will sit, and will capture issues around the implementation and effectiveness of IPS, capturing learning that will be essential for a future Phase III trial.

Co-production work throughout the study will be underpinned by the theory of partnership and the associated methodology that we have developed in previous studies (Turner-Halliday et al., 2018). Qualitative interviews and focus groups are a powerful way of developing new (and strengthening existing) relationships across groups and agencies. Qualitative interviews are particularly useful for parents or others who may need to discuss sensitive or personal topics, and focus groups are particularly useful for professional or other groups used to sharing experiences, allowing the group dynamic to facilitate the safe emergence of different perspectives. A carefully orchestrated iterative process of interviews and focus groups can give participants the space to consider and articulate their own views, then share them with other participants in a way that helps all involved to see where their common ground lies and, together, develop solutions to challenges (Turner-Halliday et al., 2018).

The co-production values of equality, diversity, access, and reciprocity (Needham, 2009) are key to the success of this process to ensure that those who have been previously silenced by structural inequalities are able to have a voice and an equal role in shaping the IPS teams.

In Phase 1, intensive mapping and modelling will be achieved through carrying out six- to eight focus groups and one to one interview per site with professional stakeholders who have knowledge and experience of working with families who are struggling and at risk of child removal from the parental home. Potential parent and child pathways will be identified and explored through interviews with GPS, health visitors, social workers, third sector organisations, etc.

Six-eight interviews with parents whose children are at risk of SW involvement (in total across Glasgow and London) to explore their experiences and needs of services.

Preliminary findings will be fed back to PC and intervention development stakeholder groups to identify any potential learning that could support intervention development.

A key component of the process evaluation in Phase 1 will be to capture the process of intervention co-development itself. The data for this will be captured as the co-development work progresses. Any data collected such as notes, will be used. In addition, we will conduct qualitative research towards the end of Phase 1 with parent collaborators to capture their views on how the process has worked for them.

Documenting coproduction/codesign processes will also provide additional data which could be useful for the Process Evaluation.

Qualitative data will be collected to explore the following topics:

- Are research procedures and measures acceptable to participating families (including experience of randomisation, level of communication from trial office, experience of consent)?
- What are parental expectations and experiences of the interventions (and to what extent were they met in later phase interviews)
- Are research procedures acceptable to referring and intervention practitioners?

Qualitative work in Phase 2 will be informed by the findings of Phase 1 and will include two-four focus groups with professionals and 16-20 interviews with IPS/services-as-usual participants to allow for greater focus on participants' experiences of services.

Through this iterative process, topics or areas of interest or debate not previously included in interview/focus group questions will be followed up on and explored further as the project progresses. This will allow for both pre-defined, and participant-led data to be gathered in a balanced way throughout the study.

Interview and focus group data will be transcribed verbatim and thematically analysed, according to the methodology of Braun and Clarke (Braun & Clarke, 2006), to identify themes including any recurrent and shared patterns of participant perceptions.

Qualitative work in phase 2 will follow MRC guidance (Moore et al., 2015) and aims to keep abreast of issues and themes uncovered in Phase 1, to explore drivers and barriers to safe/optimal IPS/SAU delivery at all trial sites. comprehensive information on the acceptability and feasibility of research procedures Data will be managed using NVivo qualitative data software and analysed thematically following Braun and Clarke's steps which include independent reading of transcripts to develop a coding frame, review and naming of codes, and development and reporting of key themes (Braun & Clarke, 2006). Findings will be fed back to PC and professional stakeholder groups (possibly using Delphi method or group feedback) in order to identify whether barriers and facilitators to services can be refined and developed into codesign responses.

Quantitative Data analysis

Quantitative analyses are not required: recruitment and retention rates will be simple percentages (Braun & Clarke, 2006).

Cost Evaluation (if appropriate)

Economic evaluation

Preliminary data will be collected to understand the costs of delivering each arm of trial including group facilitator time and grade, training costs, staff, or participant transport costs. In addition, health, personal social services, and broader educational and societal resources both within IPS and SAU will be considered, to develop an approach to build a mean cost per participant, using a bespoke 'Use of Services Questionnaire'. This will be designed specifically to examine service use relevant to this patient group from our first qualitative interviews with service users. To test data collection methods, service use diaries will be given to parents for self-completion and brought to each research assessment to support more accurate face-to-face completion of the Use of Services Questionnaire which will measure multi-sector costs. We will also ask participants detailed questions about the impact of their family's circumstances on parental employment, leisure time and about any other personal costs. We will not be constructing an economic model within this pilot trial but, instead, exploring and setting up systems to do so in future. In a future definitive study, we would explore the potential for validation of participant-report health, education and social care service use using routine health, education and social care data. In this current study, we simply intend to seek consent for this, so that routine data from this current study could potentially be pooled with data from a future definitive study (trial advisors will ensure that this process is completed in line with recent GDPR legislation).

Ethics

The University of Glasgow is the sponsor for the trial.

Ethics and regulatory approvals

A Research Ethics Committee (REC) at the University of Glasgow will review this trial. The trial is conducted according to the principles of GCP provided by Research Governance Guidelines. Annual

progress reports, end of Trial declaration, and a final report are submitted to the Sponsor and the REC within the timelines defined in the regulations.

Protocol compliance and amendment

The Investigators will conduct the trial in compliance with the Protocol given favourable opinion by the Ethics Committee. Any amendment to the project is approved by the Sponsor and funder before application to REC and R&D, unless in the case of immediate safety measures when the Sponsor is notified as soon as possible. Any deviations from the Protocol will be fully documented using a breach report form.

Ethical Consideration	Mitigation
Participant Distress	Participants may experience some upset or discomfort completing the questionnaire but, since all participants are being referred have mental health concerns, a social worker, and a multi-agency support then our information sheets will direct participants to discuss any concerns with their NHS clinician or multi agency support group.
Consent	All parents will be asked to provide informed consent for themselves and their young child before joining. Information about the study will be provided through verbal and written information. Participation in the project will be completely voluntary. Along with the consent form this information will be sent with participant’s letter. Families who have agreed to participate will be asked to complete and return a consent form for their details to be shared with the research team and stating their willingness to being considered for the study and a second consent to participate in the study prior to randomisation.
Confidentiality	Patient identifiable data will be available to the participant’s direct Social Work team, the local centre research team, and the Trial Office staff. The randomisation service at the Institute of Health and Wellbeing, University of Glasgow, will require only a date of birth, gender and minimisation criteria and is held on a secure online server and only accessible to those people working directly on the trial. Case Report Forms (CRFs) will be used to capture all data, but this data will be anonymised, and each participant will be allocated a unique Study Identity Number to remove the need for any other identifiable data.

Data Protection

A Data Protection Impact Assessment has been completed and submitted to the University of Glasgow as part of the Ethical Approval process.

Patient identifiable data will be available to the participant's direct Social Work team, the local centre research team and the Trial Office staff. The randomisation service at the Institute of Health and Wellbeing, University of Glasgow, will require only a date of birth and gender and is held on a secure online server and only accessible to those people working directly on the trial.

Case Report Forms (CRFs) will be used to capture all data, but this data will be pseudonymised and each participant will be allocated a unique Study Identity Number to remove the need for any other identifiable data.

The Data Management system for data collection and analysis will be held at the trial office in password protected files and computers and any hard copies in locked cabinets all kept in locked offices. Participant's contact details will only be used to facilitate the delivery of follow up questionnaires and any other trial information. Paper logs will not contain any information linking a trial number to any identifiable participant information. Publication of data in reports or journals will also not contain any identifiable information.

Personal data will be regarded as strictly confidential and will only be accessed by delegated members of the participants' social participants social work, clinical and research team.

To preserve pseudonymity, all trial paperwork will identify participants by their unique study Identity Number only. The trial will comply with the Data Protection Act 1998. All trial records and Site Participant confidentiality will be maintained at all times in accordance with GCP Investigator Files will be kept by the Social Worker either online or held securely in secure in a locked in locked office with restricted access. and the Social Work/NHS code of confidentiality.

Participants names and CHI/NHS numbers may be required to maintain trial records and prevent re-approaching patients who have already participated. Any paper records with patient details will be stored in a locked filing cabinet in the Social Work department. Any electronic versions (for screening logs) will be password protected and held on the secure University server (will not be held on any portable laptop devices etc).

Data collected during the course of the research is kept strictly confidential and accessed only by members of the trial team and may be looked at by individuals from the Sponsor organisation, regulatory authorities or sites where it is relevant to the participant taking part in this trial. Participants are allocated an individual trial number. Participant's details are stored on a secure database under the guidelines of the Data Protection Act. Personal data is not kept for longer than is required for the purpose for which it has been acquired. The study is compliant with GDPR and will achieve this by ensuring that all data management procedures comply with GCP and are entirely transparent to study participants.

The researchers who will be responsible for all aspects of recruiting and follow up of the participants will have access to participants' personal data. Any other member of staff will be appropriately trained and delegated this responsibility on the delegation log.

The data will be uploaded, stored, and analysed by statisticians at the University. No identifiable data will be linked to the CRF and outcome databases. 10% of all data will be screened for errors, and data will be locked before unblinding of group allocation.

Access to Social Care records by those outside the direct social care team will be required and will be accessed, with the consent of the participant, through a Data Sharing Agreement with the participating Local Authorities.

Patient identifiable data will be available to the participant's direct Social Work team, the research team and the Trial Office staff.

The trial will comply with the Data Protection Act 1998. All trial records and Site Participant confidentiality will be maintained at all times in accordance with GCP Investigator Files will be kept by the Social Worker, either online or held in a secure locked office with restricted access.

The data will be archived as per University Research governance. Anonymity will be maintained by the CI or designated individual. Data will be collected and retained in accordance with the Caldicott Principles, UK Data Protection Act 2018, and General Data Protection Regulation (GDPR). For this trial, research data will be kept for at least 10 years. Personal data (e.g., name and address, or any data from which a participant might be identified) will not be kept for longer than is required for the purpose for which it has been acquired. Documents will be reviewed by the CI before being destroyed.

In addition to working with their parents, this study will involve working with children aged 0-5, with the consent of their parents. As the purpose of the study is to improve the mental health of this group, working with them is a necessity. All IPS team members require up to date PVG scheme membership. Members of the research team who have contact with children or vulnerable families are also required to have an up-to-date membership of the PVG scheme.

Data recording and processing

UoG trial office staff will enter locally collected data into the trial database. All staff will work to ensure the data are as complete and accurate as possible. Randomisation data will be transferred to RCB using a secure file transfer protocol (SFTP), and standard data validation checks will be performed by the study statistician. Any queries will be resolved with the CI prior to database lock.

Participants have a unique participant identification number that allows identification of all data reported for each participant. Research staff can access records for all participants. All Investigators and study site staff involved with this study must comply with the requirements of the General Data Protection Regulation (or subsequent legislation), with regard to the collection, storage, processing and disclosure of personal information and will uphold the Act's core principles.

Computers used to collate the data will have measures to limit access via username and passwords.

Qualitative data management

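### The Informed consent section puts trial information, trial consent and baseline after randomisation; the rest of the protocol puts them before it

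*Protocol*

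**What the plan says.** The protocol describes two consents. In the Informed consent section, families identified by a social worker first "will be asked to give their consent before a referral is passed to the study". The same section continues: "Following randomisation, potential participants who have been selected for inclusion in the trial will receive an information sheet, Privacy Notice, and a consent form" for the trial itself. A telephone call follows, after which "consenting participants will be asked to return the freepost consent form and an appointment will be made to collect baseline data". Read in sequence, that section gives referral consent, randomisation, trial information and trial consent, then baseline.

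Other sections give the opposite order:

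- Sampling: "If they consent, families will be invited for baseline research assessments", and then "Thereafter the family will be randomised to IPS or services-as-usual and followed up at six months post randomisation".
- Randomisation and allocation: "Once baseline data is collected, participants will be randomised".
- Data Collection, Baseline: "After consent, we will arrange a baseline data collection appointment".
- Ethics, consent row of the table of considerations: families first agree to be considered and to have their details shared, then give "a second consent to participate in the study prior to randomisation".
- The short Methods summary that follows the Aims also places random allocation after the baseline assessments.

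**The concern.** Recruitment and retention are the primary outcomes of Phase 2, and the point of randomisation is the natural boundary between them. If trial consent is sought before randomisation, a family that declines is a recruitment loss. If it is sought afterwards, the same family is a loss from the randomised group. Both rates feed the judgement on whether a full-scale trial is feasible, so the boundary should not depend on which section is followed.

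Two further consequences follow from the order in the Informed consent section. The Outcomes table judges feasibility by whether 30 eligible families can be identified and randomised. That could be achieved on referral consent alone, before anyone had agreed to take part. Also, the trial office is to tell the participant and the referrer the result of randomisation (Administration arrangements post recruitment). If randomisation comes first, a family could decide on trial consent already knowing its arm.

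**Working it through.** The check is mainly one of order, so the places that fix a sequence are set side by side.

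| Protocol section | Trial consent relative to randomisation | Baseline relative to randomisation |
|---|---|---|
| Informed consent | after | after |
| Ethics table, consent row | before | not stated |
| Sampling | before | before |
| Randomisation and allocation | not stated | before |
| Methods summary after the Aims | not stated | before |
| Data Collection, Baseline | not stated (consent precedes baseline) | not stated |

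The Informed consent section stands alone, and it conflicts on both steps.

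**Does the earlier consent remove the conflict?** No. The Ethics table separates agreement to be considered from agreement to participate, and it is the second that it places before randomisation. The Informed consent section makes the same separation but places the second afterwards. Families would not be uninformed at randomisation, since they receive an information sheet before referral, but they would not yet have agreed to the trial.

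**Effect on the primary outcome.** The only sample figure is 30 families, 15 per group at 1:1; 15 + 15 = 30 is consistent and is not in dispute. Let *c* be the proportion of referred families who give trial consent, and *r* the proportion of consenting families retained.

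- Trial consent before randomisation: retained / randomised = *r*.
- Trial consent after randomisation: retained / randomised = *c* × *r*.

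The protocol gives no value of *c* for families who have already consented to referral. The range below is therefore an assumption and shows only how the formula behaves. For *r* it borrows the 72% that Sampling reports from the earlier trial.

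| Assumed *c* | Trial consenters if 30 are randomised (30 × *c*) | Retained / randomised (*c* × 0.72) |
|---|---|---|
| 0.5 | 15 | 36% |
| 0.7 | 21 | 50% |
| 0.9 | 27 | 65% |
| 1.0 | 30 | 72% |

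The two orders give the same rate only if no family declines the trial after consenting to referral.

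**The case against.** The strongest reply is that this is one stray phrase, not a rival design. Every other section that fixes the order of baseline or trial consent against randomisation puts them first. The recruitment text just before the disputed section has the information sheet and consent form posted after referral, then a call, with no randomisation in between. Words such as potential participants and selection for inclusion suit screening better than randomisation. The trial office's task list also runs from the baseline appointment to the randomisation facility and then to telling the family the result. All of this stands and makes a slip the likeliest explanation. It does not remove the conflict, because the phrase sits in the section that governs consent and nothing there corrects it. The recruitment pathway diagram is not in the text as read, so whether it settles the order cannot be told.

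Stronger readings are tempting, and the documents do not support them.

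- **That retention would fall to about 36%.** This multiplies two figures from the earlier trial. The figure of more than 50% is recruitment out of all families with a child under five entering foster care, whereas here *c* applies to families who have already consented to referral and could be much higher. The 72% is retention over 2.5 years, while this trial measures retention at 3 and 6 months. Sampling reports both as past experience, not as targets.
- **That the arms would become unbalanced by a stated amount.** No arm-specific consent rate is given, so any such split is invented.
- **That a treatment comparison would be biased.** None is planned. The baseline instruments are there to test acceptability and missingness and to supply means and standard deviations, and Quantitative Data analysis reports only simple percentages.
- **That staff would follow the Informed consent section rather than another.** The documents do not say which they would use.

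**Conclusion.** The contradiction is real and is in the current text. As written, the Informed consent section would have families randomised before they consent to the trial and before baseline, against the Ethics table, Sampling, Randomisation and allocation, and the Methods summary. What is at stake is the consent sequence itself, the boundary between the two primary outcomes, and the meaning of the 30-family indicator. That consent could be given with allocation known depends on when the result is disclosed, which the section does not say.

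The size of the effect on retention is unknown: the rate is multiplied by *c*, for which the documents give no value. The conclusion rests on the order of steps alone and on none of the assumed rates. It needs settling before the first family is randomised.

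**What to change.** In the Informed consent section, replace 'Following randomisation' with 'Following referral and initial screening'. Wording that makes the information sheet wait until eligibility is confirmed should be avoided, because the researcher confirms eligibility in the telephone call after the sheet has been received.

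State one order wherever the sequence appears: referral consent; information sheet and call, with eligibility confirmed; trial consent; baseline; randomisation; allocation disclosed. The existing provision for completing an unreturned consent form at the baseline visit fits this order, provided the form is completed before the measures are taken.

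Add two sentences: 'No family is randomised before trial consent and baseline are complete. Losses before randomisation count under recruitment, and losses after it under retention.'

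The cost is one corrected sentence, two added ones, and a check that the information sheet, the pathway diagram and the trial-office instructions agree. No data are added and the sample size does not change.
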